#### **4.11. Subject Withdrawal**

Participants who withdraw/ are withdrawn from the study, will return to standard care without negative consequences. This will be made clear in initial conversations with the research team and a study withdrawal letter will be attached to the PIS, for participants wishing to withdraw at a later stage.

#### **4.12. Data Collection and Follow up for Withdrawn Subjects**

All patients will be included in the final data analysis, by using an intention to treat analysis, thereby limiting attrition bias if patients withdraw/ are withdrawn.

## 5. Safety Reporting

For non-CTIMP reporting, please refer to the safety (other research) procedural table in Appendix 1. For Medical Device reporting, please contact the R&D Office.

The information in this section applies to HRA's expectations for safety reporting.

<https://www.hra.nhs.uk/approvals-amendments/managing-your-approval/safety-reporting/>

### 5.1. General Definitions

#### 5.1.1. Adverse Event (AE)

An AE is any untoward medical occurrence in a subject which is not necessarily caused by or related to the study. An AE can therefore be any unfavourable and unintended sign (including an abnormal laboratory finding), symptom or disease temporarily associated with study activities. There is a possibility of dizziness, coughing, tiredness and a pneumothorax with the inspiratory muscle trainer device.

#### 5.1.2. Serious Adverse Event (SAE)

An SAE fulfils at least one of the following criteria:

- Is fatal – results in death (NOTE: death is an outcome, not an event)
- Is life-threatening
- Requires inpatient hospitalisation or prolongation of existing hospitalisation
- Results in persistent or significant disability/incapacity
- Is a congenital anomaly/birth defect
- Is otherwise considered medically significant by the Investigator

A report of a Serious Adverse Events (SAEs) that are: **related to the study** (i.e. they resulted from administration of any of the research procedures) and **unexpected** (i.e. not listed in the protocol as an expected occurrence) should be emailed to the REC using the [Non-CTIMP safety report to REC form](#). These should

be sent within 15 days of the chief investigator becoming aware of the event. The completed template must also be emailed to the sponsor within **24 hours** of identifying the SAE: [[contact]](mailto:[contact])

## 6. Investigators Assessment

### 6.1.1. Seriousness

The Chief/Principal Investigator responsible for the care of the patient, or in his absence an authorised medic within the research team, is responsible for assessing whether the event is serious according to the definitions given in section 6.1.

### 6.1.2. Causality

The Investigator must assess the causality of all serious adverse events in relation to the trial treatment according to the definition given

### 6.1.3. Expectedness

The investigator must assess the expectedness of all SAEs according to the definition given. If the SAE is unexpected and related, then it needs immediate reporting.

### 6.1.4. Severity

The Investigator must assess the severity of the event according to the following terms and assessments. The intensity of an event should not be confused with the term “serious” which is a regulatory definition based on patient/event outcome criteria.

**Mild:** Some discomfort noted but without disruption of daily life

**Moderate:** Discomfort enough to affect/reduce normal activity

**Severe:** Complete inability to perform daily activities and lead a normal life

## 6.2. Notification and reporting Adverse Events or Reactions

If the AE is not defined as SERIOUS, the AE is recorded in the study file and the participant is followed up by the research team. The AE is documented in the participants' medical notes (where appropriate) and the CRF.

### **6.3. Notification and Reporting of Serious Adverse Events**

#### **Serious Adverse Event (SAEs)**

SAEs that are considered to be 'related' and 'unexpected' are to be reported to the sponsor within 24 hours of learning of the event and to the Main REC within 15 days in line with the required timeframe. For further guidance on this matter, please refer to Appendix 2

#### **6.4. Urgent Safety Measures**

The CI may take urgent safety measures to ensure the safety and protection of the trial subjects from any immediate hazard to their health and safety. The measures should be taken immediately. In this instance, the approval of the Licensing Authority Approval prior to implementing these safety measures is not required. However, it is the responsibility of the CI to inform the sponsor and Main Research Ethics Committee (via telephone) of this event immediately once identified on:

[[contact]](mailto:[contact])

#### **6.5. Annual Safety Reporting – not applicable**

#### **6.6. Procedures for reporting blinded 'unexpected' and 'related' SAEs – not applicable**

### **6.7. Overview of the Safety Reporting Process**

The information will be displayed within a table in appendix 1.

## **7. Statistical Considerations**

### **7.1. Primary Endpoint Efficacy Analysis**

To test our primary hypothesis the chi-square test will be used to assess whether IMT in combination with Prehab is effective in reducing PPCs following lung resection surgery compared with its control i.e., standard Prehab using a significance level of 0.05. 4x4 matrix.

## 7.2. Secondary Endpoint Efficacy Analysis

Secondary end points include improvement in dyspnoea score, PS, LOA, Frailty, 6MWD test, MIP and QoL. Differences between groups in categorical variables will be tested with Chi square or Fisher's exact test. For continuous data the student's t test or the Mann-Whitney U test will be used. The Wilcoxon signed rank test will be used to compare MIP and QoL at T0 and T1 and T3.

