## 2.4. Statistical Methodology and Analysis

### 2.4.1. Sample size, justification and calculations

Our literature search did not bring up a suitable RCTs on the use of POWERBreathe Inspiratory Muscle Trainer (IMT) in lung resection patients. Hence, we used the outcome data from the RCT on cardiac patients on whom POWERBreathe IMT was used and we have experience with. We acknowledge that the cardiac surgery patient population are very different and do not accurately reflect our study population (as patients undergoing cardiac surgery do not undergo lung resection). There is one RCT on the use of inspiratory spirometry used in patients undergoing lung resection in order to strengthen their diaphragm function prior to surgery (29). Inspiratory muscle training using inspiratory spirometry is different to the POWERBreathe IMT. However, the patient population and design of this RCT are more in line with our PRIMROSE Trial, making it more pertinent to use the data from this RCT instead of the RCT in a cardiac population. Hence, using the data from the lung resection patient trial, and assuming a 36.7% incidence of PPC after surgery in the control arm and using a significance level of 0.05 and a power of 80%, the online calculator estimates 50 patients are required in each arm of the study (Figure 5).

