## Data collection

QoL data using EORTC QLQ-30 questionnaire will be collected at initial assessment (T0) and on completion of Prehab (T1) as final assessment, then post-surgery at discharge (T2) and at 1 month following surgery (T3).

Subjective outcome measures data include dyspnoea score, PS, thoracoscore, frailty index (FI), LOA and objective measures include 6-minute walk distance test (6MWD) at initial assessment (T0), after every two weeks in Prehab to assess for improvement, and finally at final assessment prior to participants proceeding to surgery (T1) (14,15,30). LOA, measured using the Borg scale of perceived exertion, will be recorded as sedentary, moderately active or active and supplemented by the 6MWD. The 6MWD will be performed using a 10m corridor instead of 30m (31). A 10 metre track along a flat corridor, will be used to measure the distance walked in metres within the 6 minutes. A 10m track was used in our previously published study and proved very effective. The American Thoracic Society guidelines state a distance of 30 metres (100 foot) should be used, however this is difficult practically. It is rare to find a 30-metre corridor in a hospital that is quiet and can allow a chair to be positioned for seated rests. A 10 metre track will be better from a health and safety point of view, as well as giving patient's privacy to focus on the self-paced walk test. These above outcome measures are already standard care for all Prehab patients (14,15).

Calculating the thoracoscore for each individual for lung resection in percentage describes the mortality risk of the individual for surgery. This is already standard operating procedure (SOP) for obtaining informed consent for lung resection surgery, and will be calculated for each participant (T0 and T1) (2,32).

The maximal inspiratory pressure (MIP) for both groups will be measured using a POWERbreathe device (Figure 2) at initial assessment (T0), on completion of Prehab (T1) and at discharge (T2). Measuring MIP is not standard practice for Prehab and will be an additional and essential outcome measure. It is required to assess the progress of each individuals improvement with the Prehab. Due consideration regarding IMT contraindications in patients to avoid harm or adverse events is included in our inclusion/exclusion criteria.

Following surgery, data on PPC's and HLOS will be collected by the researcher. This is standard practice for the prehab service.

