## 7.5. Statistical Analysis

Our aim is to evaluate the impact of thoracic Prehab with IMT compared to standard Prehab in reducing post operative pulmonary complications following surgical resection in lung cancer patients in a RCT. Statistical analysis will be performed using SPSS statistical software, version 20.0 (IBM Corporation, Armonk, NY, USA). Two-sided significance tests will be used ( $\alpha \leq 0.05$ ). Data will be presented as mean and standard deviation (SD), or median and interquartile range (IQR) for variables with a skewed distribution. Differences between groups in categorical variables will be tested with Chi square or Fisher's exact test.

For continuous data the student's t test or the Mann-Whitney U test will be used. The Wilcoxon signed rank test will be used to compare MIP and QoL at T0 and T1 and T2.

Relative risk will be calculated for post operative pulmonary complications (PPCs) graded 1-V using the Clavin Dindo classification and impact of IMT on the study group compared to the control group. Assuming a 36.7incidence of PPC after surgery in the control arm and using a significance level of 0.05 and a power of 80%, 50 patients are required in each arm."

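### Section 7.2 has no test rule for ordered categories, so level of activity falls under chi-square or Fisher's test, which ignore order; an ordinal test would be a nearly free gain for the secondary outcomes.

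*Protocol*

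**What the plan says.** Section 7.2 lists the endpoints: "Secondary end points include improvement in dyspnoea score, PS, LOA, Frailty, 6MWD test, MIP and QoL". It then sorts the tests by type of variable. The first rule is "Differences between groups in categorical variables will be tested with Chi square or Fisher's exact test". The second is "For continuous data the student's t test or the Mann-Whitney U test will be used". The same pair of rules appears in the synopsis row on statistical methodology, in section 2.4.2 and in section 7.5.

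On the scales themselves, the data collection text under section 2.4.1 says that LOA "will be recorded as sedentary, moderately active or active". It groups the other measures without stating their type: "Subjective outcome measures data include dyspnoea score, PS, thoracoscore, frailty index (FI), LOA". Both that text and the schedule in section 4.5 have LOA, dyspnoea score, PS and frailty measured at T0 and again at T1, at the end of Prehab.

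The only named method that links T0 to a later value is the Wilcoxon signed rank test. It is a within-patient comparison and is limited to MIP and QoL.

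**The concern.** The two rules leave out ordered categories, and LOA is plainly one. Pearson's chi-square and Fisher's exact test return the same p-value if the three activity labels are shuffled. They spread the comparison over two degrees of freedom, whereas a shift towards more activity is a one-degree-of-freedom question. The endpoint is worded as improvement, so the direction along the scale is what the trial wants to know.

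Applied to the three-level T1 outcome, the rule also leaves the T0 level unused in the comparison between arms, although it is collected on everyone.

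At stake is sensitivity on secondary outcomes in a trial that expects about 50 analysed per arm. A real shift in LOA would be missed more often than necessary, while a better test is already in the plan. For dyspnoea score, PS and frailty, the open assignment lets the analyst choose between two tests of different power after seeing the data.

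**Working it through.** **1. Number per arm.** The protocol states: "using a significance level of 0.05 and a power of 80%, the online calculator estimates 50 patients are required in each arm of the study". That figure is for the primary outcome, "assuming a 36.7% incidence of PPC after surgery in the control arm". The intervention-arm rate is not in the text, so 50 cannot be fully reproduced. The pooled two-proportion formula gives 49 per arm at 12.5% and 51 at 13%, so 50 fits an intervention rate near there. Recruitment reproduces: 100 / (1 − 0.25) = 133.3, rounded up to 134. I use 50 per arm here only as the analysed number. The protocol states no power for any secondary outcome.

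**2. Test settings.** Alpha is 0.05, and section 7.5 says "Two-sided significance tests will be used".

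**3. Assumptions not in the documents.** These are the category shares, a proportional-odds shift, odds ratios (OR) of 1.5 to 3, and four or five levels for dyspnoea score and PS. Only the three levels of LOA come from the protocol.

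**4. Analytic check.** An ordinal test with 1 df and 80% power has noncentrality (1.960 + 0.842)² = 7.85. Pearson's test on k levels, at the same noncentrality, has k − 1 df:

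| Levels | df | Critical value | Power | Loss from 80% |
|---|---|---|---|---|
| 3 | 2 | 5.99 | 70.9% | 9.1 |
| 4 | 3 | 7.81 | 64.5% | 15.5 |
| 5 | 4 | 9.49 | 59.5% | 20.5 |

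**5. Simulation.** The shift divides each cumulative odds in the control arm by OR. Example with equal thirds and OR 2: control cumulative probabilities 1/3 and 2/3 have odds 0.5 and 2. Halved, these are 0.25 and 1, giving 0.20 and 0.50, so the shares become 0.20, 0.30, 0.50. Power of Pearson's chi-square against tie-corrected Mann-Whitney, 50 per arm, 20,000 runs per setting:

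| Control shares | OR | Chi-square | Mann-Whitney | Loss (points) |
|---|---|---|---|---|
| 3 levels, equal thirds | 1.5 | 15.6% | 19.4% | 3.8 |
| | 2 | 36.3% | 45.9% | 9.6 |
| | 2.5 | 57.7% | 68.2% | 10.5 |
| | 3 | 73.4% | 81.9% | 8.5 |
| 4 levels (0.20, 0.45, 0.25, 0.10) | 1.5 | 12.5% | 19.5% | 7.0 |
| | 2 | 30.2% | 45.3% | 15.1 |
| | 2.5 | 50.3% | 68.1% | 17.8 |
| | 3 | 67.3% | 83.0% | 15.7 |
| 5 levels (0.10, 0.30, 0.30, 0.20, 0.10) | 1.5 | 11.6% | 20.1% | 8.5 |
| | 2 | 27.8% | 47.9% | 20.1 |
| | 2.5 | 46.9% | 70.4% | 23.5 |
| | 3 | 65.0% | 85.0% | 20.0 |

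Uneven three-level shares (0.30, 0.45, 0.25) give nearly the same: about 36% against 46% at OR 2 and 57% against 68% at OR 2.5. Over all three-level share sets tried, the loss is 9 to 11 points at OR 2 to 2.5 and about 4 at OR 1.5.

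**6. Sensitivity to the number per arm.** With 40 to 67 per arm and OR 2 to 2.5, the loss is about 8 to 11 points for three levels and 14 to 24 for four or five.

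**7. Checks in the other direction.** With no difference between arms, both tests reject about 5% of the time. For a split into improved or not improved (40% against 65%), both tests have 73.8% power, so the loss is 0. For a non-monotone difference (0.30, 0.40, 0.30 against 0.15, 0.70, 0.15), chi-square has 79% power and Mann-Whitney 6%.

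**The case against.** Four objections carry weight.

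- **Scope.** A reader might infer that dyspnoea score, PS and frailty are also assigned to chi-square. The documents do not say so. They call two of these a score and an index, apply numeric cut-offs to all three in the referral criteria, and never class them as categorical. An analyst could send them to Mann-Whitney under the rule for continuous data. This stands: only LOA is clearly caught.
- **Meaning of improvement.** A reader might infer that the plan cannot separate improvement from worsening and discards T0 altogether. That does not follow. If improvement means improved or not improved since T0, the outcome is binary, directional and built from T0, and chi-square or Fisher's test is usual. The protocol does not say which meaning applies, so the criticism holds for the three-level outcome only.
- **Size.** A reader might take a loss of 10 to 24 points as a property of the plan, with nothing gained in return. It depends on assumed levels, shares and effect. The upper end belongs to outcomes whose assignment is unclear, and the general chi-square does detect non-monotone differences that a rank test misses.
- **Detail.** Test choice for each secondary outcome is often left to the statistical analysis plan, and LOA is supplemented by the six-minute walk distance, which falls under the rule for continuous data. The first part does not remove the point: the protocol itself states the two-way rule in four places, and LOA falls on the wrong side of it. The second softens the consequence.

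**Conclusion.** The point holds as an improvement to the secondary analyses. As written, LOA goes to a test that ignores order and, on the three-level outcome, does not use T0. With 50 per arm and a proportional-odds shift, the cost is about 9 to 11 points of power at OR 2 to 2.5 and about 4 at OR 1.5. For dyspnoea score, PS and frailty the fault is an unclear assignment. The figure of 15 to 24 points for four or five levels at OR 2 to 2.5 applies only if such scores were sent to chi-square.

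These sizes rest on assumed category shares and odds ratios and, beyond LOA, on assumed level counts. Type I error is not inflated, and the primary analysis and sample size are not affected. Nothing here makes the planned test invalid; it is less sensitive than it need be to the kind of change that the endpoint names.

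**What to change.** In section 7.2, state that LOA, and dyspnoea score, PS and frailty where they are treated as ordered scores, are compared between arms at T1 with a proportional-odds model on arm and T0 category, reporting the common odds ratio with its 95% confidence interval. As a minimum, assign them to Mann-Whitney U, which is already in the plan but would not by itself use T0. Keep chi-square or Fisher's exact test for binary and nominal outcomes. Make the synopsis, section 2.4.2 and section 7.5 match.

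The cost is about one sentence in each place. No new data or visits are needed, and the methods are available in the software already named. The one drawback is less sensitivity to non-monotone differences, which are not what an endpoint worded as improvement is looking for.

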#### **1.4. Rationale and Risks/Benefits**

We hypothesise that prior to surgery, an IMT device in combination with a standard Prehab program compared with Prehab alone, will further improve the strength and endurance of the surgical NSCLC patients' inspiratory muscles used for breathing. By doing so, IMT with Prehab will allow patients who have undergone lung resection surgery to clear their airway of secretions more effectively in the post-operative period and provide a significant benefit to patients by lowering their risk of developing PPCs and shorten their HLOS after surgery, improve their overall QoL and additionally reduce NHS costs.

There are no expected risks to participants of this trial. Our previous studies, have shown that thoracic Prehab safely optimises patients for surgery (14,15). Good tolerance with IMT devices have been reported, although can cause feelings of fatigue (27,28).

---

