## 4.4. Schedule of Treatment for each visit

On initial face-to-face assessment, conducted within 5 working days of receiving the referral for Prehab, the research team will provide participants with participant information sheet and informed consent form. Informed consent to participate will be obtained. Patients can bring carers to the face-to face assessment if they wish.

**Control group:** The control group will receive a standard Prehab protocol.

**Standard Prehab protocol** is described in our previous pragmatic study published in the Lancet journal *Journal of Clinical Medicine* (15). Prehab will be provided to participants over 2–4 weeks with supervised once weekly sessions ~~with supervised two weekly sessions~~ of 70 minutes each, along with exercises for patients to carry out at home. Three weeks is an anticipated average based on published data and urgency to proceed to surgery as cancer can grow and become inoperable by six weeks. This area is much debated in the Prehab literature. Our aim is to ensure as many patients benefit with Prehab followed by lung resection surgery as possible, with broader health benefits to patients and a positive impact on their quality of life. Our previous study showed that patients can be physically optimised safely in as little as two weeks (15). However, for patients who may be slower to respond there is scope in our program for a more prolonged course of Prehab if required.

Outcome measures will be collected every two weeks on the Prehab programme by the research team, which is standard practice. As patients become eligible, they will withdraw from Prehab and proceed to surgery once a surgical date is confirmed. Management of individuals deemed unfit for surgery will be discussed at the individuals' local lung cancer MDT for consideration of alternative treatment options namely, radiotherapy, systemic anti-cancer treatment or palliative care.

**Respiratory muscle training and breathing exercises.** Both groups will receive incentive spirometry devices pre operatively. Participants will be encouraged to practice and train with the spirometer device three times daily, so can use the spirometer effectively post operatively. This is standard care as spirometers aid lung volumes and removal of secretions post operatively.

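### The only test named for MIP and QoL is a within-patient one, and the protocol does not say which analysis compares the arms on them

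*Protocol*

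**What the plan says.** The hypothesis in section 1.4 is comparative: adding the device to Prehab, against Prehab alone, "will further improve the strength and endurance of the surgical NSCLC patients' inspiratory muscles used for breathing". The Data collection part of section 2.4.1 has MIP measured in both groups at T0, T1 and T2 and says "Measuring MIP is not standard practice for Prehab and will be an additional and essential outcome measure".

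Section 7.2 sets out the secondary efficacy analysis in four steps:

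- the endpoints: "Secondary end points include improvement in dyspnoea score, PS, LOA, Frailty, 6MWD test, MIP and QoL"
- categorical data: "Differences between groups in categorical variables will be tested with Chi square or Fisher's exact test"
- continuous data: "For continuous data the student's t test or the Mann-Whitney U test will be used"
- MIP and QoL by name: "The Wilcoxon signed rank test will be used to compare MIP and QoL at T0 and T1 and T3"

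The last three steps recur in the same order in the synopsis, section 2.4.2 and section 7.5. In the synopsis and section 7.5 the last visit differs: "The Wilcoxon signed rank test will be used to compare MIP and QoL at T0 and T1 and T2".

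On what both arms receive, section 4.4 says "Both groups will receive incentive spirometry devices pre operatively. Participants will be encouraged to practice and train with the spirometer device three times daily". It places this under a heading on respiratory muscle training, alongside two to four weeks of supervised and home exercise.

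**The concern.** The signed-rank test pairs two visits in the same patient and has no term for arm. It asks whether MIP or QoL changed, not whether it changed more with the device. The control arm is active, so a rise in its MIP is plausible by design, and a before-after rise in the IMT arm would not separate the device from Prehab.

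An analyst could follow the sentence that names MIP and QoL, report before-after p-values by arm, and have met the protocol to the letter. Significance in one arm and not in the other would then invite a conclusion that no test of the difference supports. MIP is the measure closest to the mechanism hypothesised in section 1.4, so its analysis should bear on the comparison. The text also does not say whether the signed-rank test is run per arm or on both arms pooled, or which pairs of the three listed visits are compared.

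**Working it through.** **Plan figures.** The protocol gives no SD, effect size or power for MIP or QoL, so there is no figure of its own to reproduce on this point. It does give 50 analysed per arm, a two-sided 0.05 level, and 67 randomised per arm with 25% attrition: 50 / (1 - 0.25) = 66.7, which rounds up to 67.

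**Assumptions (not in the protocol).** MIP SD 25 cmH2O at each visit, and T0-T1 correlation r of 0.6 to 0.8.

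**Step 1. No IMT effect, both arms gain the same amount.** The SD of the within-patient change is sqrt(2 × 25² × (1 - r)), which is 22.4, 19.4 and 15.8 at r = 0.6, 0.7 and 0.8. Let p be the chance that a paired test is significant in one arm of 50. It comes from a noncentral t distribution with noncentrality gain × sqrt(50) / SD of change (a paired t approximation to the signed-rank test). The arms are independent, so the chance of a significant IMT arm with a non-significant control arm is p(1 - p).

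| r | Gain (cmH2O) | p | p(1 - p) |
|---|---|---|---|
| 0.6 | 5 | 0.34 | 0.22 |
| 0.6 | 6.5 | 0.52 | 0.25 |
| 0.6 | 8 | 0.70 | 0.21 |
| 0.7 | 5 | 0.43 | 0.25 |
| 0.8 | 5 | 0.59 | 0.24 |
| 0.8 | 8 | 0.94 | 0.06 |

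So the IMT arm alone would show a significant rise in 34% to 94% of trials, and the misleading pattern would occur in about 6% to 25%.

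**Step 2. Check with the signed-rank test itself.** This simulation used 50 per arm, 3,000 runs, and gains in SD units. With r = 0.5 and a gain of 0.3 SD in both arms, the IMT arm is significant in 53% of trials and is the only significant arm in 23.6%. With r = 0.7 and a gain of 0.2 SD, the figures are 41% and 23.9%. Over all settings tried, a Mann-Whitney test of change between arms rejected in 4.3% to 5.3% of trials, as it should with no effect.

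**Step 3. Power for a true between-arm difference of 10 cmH2O.** This uses a two-sample noncentral t with 50 per arm and noncentrality 10 / sqrt(2V/50), where V is the outcome variance that applies.

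| Analysis | V | r = 0.6 | r = 0.7 | r = 0.8 |
|---|---|---|---|---|
| T1 value, unadjusted | 625 | 0.51 | 0.51 | 0.51 |
| Change from T0 | 1250(1 - r) | 0.60 | 0.72 | 0.88 |
| T1 adjusted for T0 | 625(1 - r²) | 0.70 | 0.79 | 0.91 |

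Adjustment gains about 10, 7 and 3 percentage points over change scores. Over unadjusted T1 values it gains 19 to 40 points.

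**The case against.** The strongest reply is that section 7.2 already holds a between-arm test. It lists MIP and QoL as endpoints and then gives two-sample tests for continuous data. MIP is continuous, and nothing says that the signed-rank sentence replaces those tests. This largely stands. A reader might infer that the protocol has no between-arm test for MIP, so that no change could ever be credited to IMT, but the documents do not support that. What remains is that the only test naming these two endpoints is within-patient, and the protocol never says that the two-sample test carries their efficacy claim.

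A reader might also infer that T0 is ignored. That is not shown. The endpoint is worded as improvement, which may mean change from T0, and a test of change uses T0. The text leaves this open, and no stated analysis adjusts for T0. An unadjusted comparison in a randomised trial is valid, so adjustment improves precision and does not correct an error. Covariate adjustment is often left to an analysis plan, which is not at hand here.

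A reader might count every trial in which exactly one arm is significant, which is 2p(1 - p). Half of those have only the control arm significant, which nobody would take as evidence for the device, so p(1 - p) is the relevant figure.

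Finally, section 2.4.1 gives MIP a within-patient purpose, namely following each person's progress, and a paired test suits that purpose. No passage says that a within-arm p-value will be the evidence for IMT. That is fair, but the sentence sits under an efficacy heading.

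**Conclusion.** The point holds as a defect of specification. The test the protocol names for MIP and QoL cannot address the comparative hypothesis, and the general test that could address it is not identified as their efficacy analysis or defined as a test of the later value or of change.

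If within-arm results were taken as evidence, the misleading pattern would arise in about 6% to 25% of trials with no IMT effect. Naming a T0-adjusted contrast would add about 3 to 10 points of power over change scores, and more over unadjusted T1 values. These sizes rest on an assumed SD, correlation, gains and true difference, and on 50 patients per arm with MIP data; the qualitative point does not. Both endpoints are secondary. The primary analysis in section 7.1 compares the arms and is unaffected.

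**What to change.** In the synopsis and sections 2.4.2, 7.2 and 7.5, state that:

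- the MIP efficacy analysis is the between-arm difference at T1, from a linear model on arm and the T0 value, with a 95% CI
- the QoL efficacy analysis is the between-arm difference in one pre-named QLQ-C30 score at one pre-named visit at which it is collected, from the same kind of model
- other visits and scales are supportive, which avoids a string of equal-ranking tests
- the signed-rank test is a within-arm description, and no claim about IMT rests on it.

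The same edit should reconcile the last visit in the signed-rank sentence (T2 in two places, T3 in the other two), because the schedule in section 4.5 collects no MIP at T3.

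The cost is analysis wording, plus the decision on which QoL score and visit to name. T0 values are already collected in both arms and SPSS fits the model. The primary endpoint and sample size do not change.
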